3.3.2 Safety

Safety endpoints to be used in this study will include:

- 1. Proportion of subjects with a treatment-emergent adverse event (TEAE) or a clinically significant laboratory abnormality (overall and of any given type);
- 2. Proportion of subjects who discontinue due to an adverse event (AE) (either treatment-emergent or clinically significant laboratory abnormality).

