7.0 STUDY OR SITE TERMINATION AND SUBJECT DISCONTINUATION

7.1 ADVERSE EVENT STOPPING RULES

If a subject experiences an AE that, in the judgment of the investigator, the sponsor, or the medical monitor, presents an unacceptable consequence or risk to the subject, the subject may be discontinued from the study.

If a participant develops cholangitis or an inflammatory bowel disease (IBD) flare twice during the trial, then the patient should be discontinued from study drug, but maintained in the study for safety follow-up.

- Cholangitis is defined as cholestasis and systemic inflammation demonstrated by clinical signs or blood test results in addition to biliary manifestations demonstrated by imaging.
- Inflammatory bowel disease flare-ups are defined as unexpectedly frequent and/or urgent bowel movements, diarrhea, bloody stools or abdominal pain, not requiring systemic immunosupression with a corticosteroid or a biological agent.

If a participant develops a dominant stricture or an IBD flare requiring new or increased of immunosupressive therapy (systemic corticosteroids or biologics), then the patient should be discontinued from study drug, but maintained in the study for safety follow-up.

• A dominant stricture is defined as intervention due to symptoms, compelling imaging results, or a prominent increase in liver biochemical markers.

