5.1. SUBJECT DISPOSITION, DEMOGRAPHIC AND BASELINE CHARACTERISTICS, AND EXPOSURE

Subject disposition will be presented for all subjects randomized in Period 1. Subjects will be summarized in aggregate for the number of screen failures, the number subjects in the Safety and mITT populations, the number of subjects completing the study and each period, the reasons for early discontinuation at any point, and the number of subjects discontinuing by treatment taken when discontinuation occurred. Disposition and all listings will be presented for the subjects randomized (in Period 1).

Demographic data and baseline characteristics including age, sex, race, height at screening, weight at screening, body mass index (BMI), IBD diagnosis as randomized, UDCA status when entering the study, and protocol version will be summarized using descriptive statistics for the Safety population, and will be presented by treatment group, as treated for Period 1. This information will be reviewed for baseline differences, but no statistical testing will be performed.

Data on drug accountability and total amount of study drug received will be summarized by Period and treatment type according to treatment received in each period. Total study drug exposure within each period will be calculated as the sum of tablets dispensed over the duration of time a subject was on a given study drug within said period – the amount of that study drug returned within said period x the number of mg in the tablets (i.e. 0 mg for Placebo, 125 mg for 500 mg Arm, and 250 mg for 1000 mg Arm). Total exposure over the study period will also be summarized as the sum of the mg taken over all periods.

Weeks of exposure in each period will be calculated as (date of first dose – date of last dose + 1)/7 in the period. Study drug compliance will then be calculated as the number of tablets taken (as defined above) divided by the number of expected tablets to be taken in the period (weeks of exposure x 56) and then x 100 to convert to percentage. Weeks of exposure and study drug compliance will only be presented by period.

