5.3. SAFETY

5.3.1. Adverse Events

AEs will be mapped to a Medical Dictionary for Regulatory Activities (MedDRA) version 20.1 preferred term (PT) and system organ classification (SOC). If a subject experiences multiple events that map to a single preferred term, the greatest severity grade according to the Common Terminology Criteria for Adverse Events (CTCAE) Version 4.0 will be assigned to the preferred term for the appropriate summaries. Should an event have a missing severity or relationship, it will be classified as having the highest severity and/or assumed related to study medication. The overall occurrence of any TEAEs, TEAE related to study drug, severe TEAEs, serious TEAEs, TEAE leading to discontinuation of study drug, and TEAE leading to death, alongside individual counts of each respective TEAE. The occurrence of TEAEs will be summarized by treatment group by SOC, and PT based on the treatment taken at AE start date. Summaries of the total number of subjects receiving each treatment and the average weeks of exposure for each treatment will be provided for context.

Separate summaries of each TEAE by period, TEAEs leading to the discontinuation of study, TEAEs related to study drug, and serious TEAEs will be generated and summarized by SOC and PT. The occurrence of TEAEs will be summarized by treatment group by SOC, PT, and Severity will also be summarized.

All adverse events reported will be listed for individual subjects showing verbatim term, PT and SOC. All AEs that occurred prior to the initiation of study treatment will be excluded from the tables but will be included in the listings.

Missing onset dates will be imputed as previously outlined in [Section 3.3.5](#) as required to determine treatment-emergent events.

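### SAP 5.3.1 counts drug discontinuations in the AE overview but study discontinuations in the SOC/PT table, so read literally the drug stops required by Protocol 7.1 are in the first and not the second

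*SAP*

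**What the plan says.** SAP 5.3.1 describes two kinds of discontinuation output.

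- The overview of TEAEs includes rows for "TEAE leading to discontinuation of study drug, and TEAE leading to death". The criterion is stopping study drug.
- The next paragraph lists separate summaries: "TEAEs leading to the discontinuation of study, TEAEs related to study drug, and serious TEAEs will be generated and summarized by SOC and PT". The criterion is stopping the study.

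Protocol 7.1 has two rules under which these differ. The first begins "If a participant develops cholangitis or an inflammatory bowel disease (IBD) flare twice during the trial", the second "If a participant develops a dominant stricture or an IBD flare requiring new or increased of immunosupressive therapy". Both end the same way: "then the patient should be discontinued from study drug, but maintained in the study for safety follow-up". The opening paragraph of 7.1 has a different route, under which a subject with an AE judged to pose an unacceptable risk may be taken out of the study altogether.

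Protocol 3.3.2 gives as its second safety endpoint the proportion of subjects who discontinue because of an AE. It does not say whether that means drug or study. SAP 5.1 plans a disposition summary with "the reasons for early discontinuation at any point, and the number of subjects discontinuing by treatment taken when discontinuation occurred", also without saying which.

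**The concern.** The SOC/PT discontinuation table is where a reader looks to see which kinds of event made subjects stop treatment. In many trials, stopping drug and leaving the study nearly coincide, and loose wording would do little harm. Here the protocol keeps certain subjects in the study after drug is stopped, and it does so for named biliary and bowel events. A table filtered on leaving the study would pass over those stops and keep AE stops in which the subject also left.

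Tolerability and IBD activity are secondary objectives, so the reasons for stopping drug matter. The overview row and the SOC/PT table could also show different totals with no explanation of the difference.

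**Working it through.** The plan gives no figure to reproduce and no arithmetic applies. The check is to follow each AE-related stopping route in Protocol 7.1 through the tables in SAP 5.3.1 as worded.

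| Route in Protocol 7.1 | Study drug | Study participation | Overview row (drug) | SOC/PT discontinuation table (study) | Other SOC/PT TEAE tables |
|---|---|---|---|---|---|
| Second cholangitis or second IBD flare | stopped | continues | counted | not counted | event appears |
| Dominant stricture, or flare needing new or increased immunosuppression | stopped | continues | counted | not counted | event appears |
| AE judged an unacceptable risk, subject removed from study | stopped | ends | counted | counted | event appears |

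The first two rows are where the two outputs part. The table takes the triggering event to be recorded as a TEAE.

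Next, does any other planned output link a drug stop to its event type?

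- The overall, by-period and by-severity TEAE tables show the events but do not mark which led to stopping drug.
- The related and serious TEAE tables select on other attributes.
- The overview is described as "TEAE leading to discontinuation of study drug, and TEAE leading to death, alongside individual counts of each respective TEAE". The natural reading is a number of events beside the number of subjects in each category. No SOC or PT split is named for it.
- Disposition (SAP 5.1) gives reasons for discontinuation, not SOC or PT.
- The AE listing is specified as verbatim term, PT and SOC. Action taken with study drug is not named.

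So the separate summary in SAP 5.3.1 is the only planned table that breaks discontinuations down by event type, and its stated criterion leaves out the first two routes.

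**The case against.** The strongest reply is that a word has been dropped. The two lists in SAP 5.3.1 run in parallel (related, serious, leading to discontinuation), and the natural match for the overview row is discontinuation of study drug. That may well be right. But nothing in the SAP corrects the phrase, and SAP section 5 relies on independent programming for verification, so two programmers could reasonably choose different flags. If it is a slip, the same edit cures it.

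A second reply is that Protocol 7.3 allows removal from the study for reasons described in 7.1 to 7.3, so some of these subjects might leave the study after all. This narrows the point, since not every such stop need be lost. It does not remove it, because 7.1 specifically keeps these subjects in the study.

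A third reply is that few subjects will be affected. Cholangitis, or a flare without new or increased immunosuppression, stops drug only on its second occurrence within an 18-week study. The exclusion criteria remove ascending cholangitis within 60 days of screening, recent colitis flares needing intensified therapy (90 days), and suspected new dominant strictures within 1 year. With about 60 subjects planned in SAP 1.1, the count may be small or zero. This stands as a limit on size.

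A reader might also infer more than the documents support:

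- *That the events disappear from safety reporting.* They do not; they remain in the general, by-period and severity tables and in the listing. SAP section 5 lists all collected data, so the link to the drug stop might be rebuilt by hand.
- *That the second safety endpoint is under-counted.* It asks for a proportion with no split by event type, and the overview row can supply it.
- *That the pregnancy and liver rules add to the gap.* Protocol 5.1.6 says pregnancy is not recorded as an AE, and Protocol 6.9 requires interruption of drug, which is not in itself discontinuation.
- *That such subjects would be reported as completers.* SAP 5.1 does not define completion, so this cannot be shown.

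**Conclusion.** The inconsistency is real and its reach is narrow. As written, SAP 5.3.1 uses one criterion for the overview and another for the SOC/PT discontinuation table, and Protocol 7.1 makes them select different subjects. What is lost is the link between event type and drug stop, in one descriptive table, for stops under the two 7.1 rules where the subject stays in the study. No efficacy analysis, hypothesis test or overall discontinuation proportion is affected.

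The size cannot be put as a number, because the documents give no expected frequency for these stops. The conclusion rests on a literal reading of the SAP and on two assumptions: that the triggering event is recorded as a TEAE, and that the subject stays in follow-up as 7.1 directs. Protocol 6.1 does not count expected disease progression as an AE unless it is more severe than expected, so a stricture regarded that way would be in neither output. The point concerns reporting only and takes no position on the stopping rules themselves.

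**What to change.** In SAP 5.3.1, define the SOC/PT discontinuation summary as TEAEs leading to discontinuation of study drug, matching the overview. If TEAEs leading to study discontinuation are also of interest, give them a second, separately titled table. State in the SAP that the second safety endpoint in Protocol 3.3.2 is evaluated on study-drug discontinuation.

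Two additions are optional: show action taken with study drug in the AE listing, and add a disposition row in SAP 5.1 for subjects who stopped drug early but remained in the study.

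The cost is SAP wording and one table filter. The overview row already needs a flag for drug discontinuation, so the core change needs no new data.

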5.3.2. Clinical Laboratory Assessments, Vital Signs, Height, and Weight

Descriptive summaries of selected (quantitative) clinical laboratory results and change from Baseline will be presented by time point and overall treatment groups. Baseline will be the last value observed prior to dosing in Period 1. For more detail on how safety tables will be presented, see [Section 3.3.6](#).

Shift tables (low, normal, high) for change from Baseline to Week 6 in Period 1, and from Week 6 to Week 12 in Period 2 will be presented for all appropriate clinical laboratory parameters by treatment group in Period 1 and Period 2 (excluding efficacy only groups).

Descriptive summaries and change from Baseline in vital signs data, as well as height and weight, will be presented by time point and overall treatment groups, similar to the presentation of clinical laboratory assessments.

Values for all safety variables will be listed by subject and visit (as applicable).

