1.1. STUDY OVERVIEW

Protocol HTD1801.PCT003 is a Phase 2, randomized, double-blind study which consists of a placebo- and dose-controlled parallel group period, a dose-controlled extension period, and a placebo-controlled randomized withdrawal period with the intent of comparing multiple doses of investigational product (HTD1801) to placebo. Approximately 60 patients with Primary Sclerosing Cholangitis (PSC) will be enrolled as subjects. Upon confirmation of eligibility, subjects will be randomized in Period 1 in a 1:1:1 ratio, stratified by inflammatory bowel disease (IBD) diagnosis and ursodiol (UDCA) status, to one of the following treatment arms:

- **Treatment Arm 1:** HTD1801 500 mg twice daily (BID)
- **Treatment Arm 2:** HTD1801 1000 mg BID
- **Treatment Arm 3:** Placebo BID.

Subjects will receive the treatment to which they are randomly assigned for 6 weeks during the first period.

In response to the COVID-19 pandemic, enrollment into the study was prematurely stopped on 25th March 2020. This impacted 3 subjects who had been randomized but had not yet initiated dosing. There may be additional restrictions associated with COVID-19 that may impact sites' ability to schedule subjects for in-clinic visits and thus, complete all protocol-required assessments. These will be noted as protocol deviations related to COVID-19 should they occur. These measures were put into place following the issuance of the FDA Guidance on Conduct of Clinical Trials of Medical Products during COVID-19 Pandemic (March 2020 and April 2020).

See [Section 3.2](#) for additional details on Period 1 randomization.

Following the completion of the first period, subjects are eligible to enroll in Period 2 which is a 6-week extension period. During this period, subjects who were previously randomized to 500 mg or 1000 mg BID in Period 1 will continue to receive the same dose. Subjects who were previously randomized to placebo will be randomized in a 1:1 ratio to receive 6 weeks of either 500 mg or 1000 mg BID. This period will continue to be double-blind.

Following the completion of Period 2, the 6-week treatment extension period, all subjects will be randomized in a 1:1 ratio to either continue on the active treatment they received in the second period or be assigned to placebo.

An independent Data and Safety Monitoring Board (DSMB) will provide additional safety oversight.

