Following their completion of Period 1, subjects will enroll in a 6-week extension period in which subjects previously randomized to 500 mg or 1000 mg BID will continue for 6 more weeks at that previous dose, while subjects previously randomized to placebo will be randomly assigned to receive 6 weeks of either 500 mg or 1000 mg BID.

Period 3: Randomized withdrawal

Following their completion of Period 2, subjects will enroll into a 6-week randomized withdrawal period in which all subjects will be randomly assigned in a 1 to 1 ratio to either continue on the active treatment they received in Period 2, or be assigned to placebo so that 50% of the subjects remain on the experimental treatment at the previous dose, and 50% will receive placebo.

All subjects and study personnel will remain blinded as to the treatment administered throughout the study with the exception of an unblinded statistician who will develop the randomization list with the expanded strata and an unblinded EDC designer who will load the completed randomizations

into the EDC system. All study test drug will be provided in matching white tablets, four to a bottle, two bottles to be administered each day, one in the morning and one in the evening. A 45-day supply will be provided to each subject at each visit to cover the next 6-week period with an additional 3 days of coverage to provide for possible scheduling conflicts.

In this double-blind study, if a medical emergency occurs and a decision about a subject's condition requires knowledge of the treatment assignment in order to properly treat the subject, the study blind may be broken for that specific subject only. Ideally, the decision to break the blind for this one subject should only be made after consultation with the Medical Monitor or Sponsor Representative.

Any broken blind must be clearly justified and explained by a note in the subject's source documents.

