5. STATISTICAL METHODS

Descriptive statistical methods will be used to summarize the data from this study, with hypothesis testing performed for the primary and other selected efficacy endpoints. Unless stated otherwise, the term “descriptive statistics” refers to number of subjects (n), mean, median, standard deviation (SD), minimum and maximum for continuous data and frequencies and percentages for categorical data. Additional statistical methods include mixed model repeated measures (MMRM), Student’s t-test (unpaired and paired), and Fisher Exact test. All data collected during the study will be included in data listings. Unless otherwise noted, the data will be sorted first by subject number, and then by Period and date within each subject number.

The term ‘treatment group’ refers to all subjects on the same dosing regimen. Efficacy and Safety tables will include only treatment groups that are present in the respective period being summarized. Safety tables will include all treatment groups. The treatment groups will apply for each period:

- Overall – Subjects will be summarized according to the period 1 treatment for demographic and screening information, or according to the actual treatment at the time of event or visit for safety summaries. AE summaries will use this format as well for the by period summaries.
 - Placebo
 - HTD1801 500 mg BID
 - HTD1801 500 mg BID
- Period 1 – Subjects will be summarized according to Period 1 treatment
 - Placebo
 - HTD1801 500 mg BID
 - HTD1801 500 mg BID
- Period 2 – Subjects will be summarized according to the Period 1 and Period 2 treatments
 - HTD1801 500 mg BID to HTD1801 500 mg BID
 - Placebo to HTD1801 500 mg BID
 - All HTD1801 500 mg BID (efficacy only)
 - HTD1801 1000 mg BID to HTD1801 1000 mg BID
 - Placebo to HTD1801 1000 mg BID
 - All HTD1801 1000 mg BID (efficacy only)

- Period 3 – Subjects will be summarized according to the Period 2 and Period 3 treatments
 - HTD1801 500 mg BID to HTD1801 500 mg BID
 - HTD1801 1000 mg BID to HTD1801 1000 mg BID
 - HTD1801 500 mg BID to Placebo
 - HTD1801 1000 mg BID to Placebo
 - All Active to Placebo

All statistical tests will be two-sided with an alpha level of 0.05.

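### After Week 6 the laboratory and vital-sign safety summaries group subjects by current treatment, which mixes new with continuing exposure in Period 2 and pools both withdrawn doses under one Placebo column in Period 3

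*SAP*

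**What the plan says.** SAP 5.3.2 sets the layout of the laboratory tables: "Descriptive summaries of selected (quantitative) clinical laboratory results and change from Baseline will be presented by time point and overall treatment groups". The reference value is fixed once for the whole study: "Baseline will be the last value observed prior to dosing in Period 1". Vital signs, height and weight follow the same layout; they "will be presented by time point and overall treatment groups, similar to the presentation of clinical laboratory assessments".

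SAP 5 defines the overall groups. For safety they are formed "according to the actual treatment at the time of event or visit for safety summaries", with one Placebo group and no reference to what was taken before. (The printed list shows 500 mg twice; I read the second entry as 1000 mg.)

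Treatment changes twice during the study. In Period 1, "subjects will be randomized in Period 1 in a 1:1:1 ratio" (SAP 1.1). In Period 2, "subjects who were previously randomized to 500 mg or 1000 mg BID in Period 1 will continue to receive the same dose", whereas those who had received "placebo will be randomized in a 1:1 ratio to receive 6 weeks of either 500 mg or 1000 mg BID". In Period 3 everyone is randomised 1:1 to stay on the Period 2 dose or to go to placebo (SAP 1.1 and 3.2).

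SAP 5 also lists sequence groups: Period 1 to Period 2 treatment for Period 2, and Period 2 to Period 3 treatment for Period 3. SAP 5.3.2 applies the Period 2 list to the laboratory shift tables, which stop at Week 12, but names the overall groups for the descriptive tables. Its cross-reference to SAP 3.3.6 leads to visit windows and defines no treatment groups.

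**The concern.** A reader of a by-visit table expects each column to follow the same people. Here it does not. The Placebo column holds untreated subjects up to Week 6, nobody at Weeks 8 to 12, and only previously treated subjects at Weeks 14 to 18. Each dose column gains subjects after Week 6 and loses half of them after Week 12. A movement in a column mean across those boundaries may come from the change in membership.

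Two pieces of information are lost. In Period 2, subjects new to the drug cannot be told apart from those already on it for six weeks. In Period 3, the randomised comparison within each dose (continue against withdraw) cannot be read, because the withdrawn subjects from both doses share one column.

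Safety over 18 weeks is a secondary objective (SAP 2). ALT and AST drive the liver monitoring algorithm in Protocol 6.9, yet they have no other grouped summary in Period 3, and the AST/ALT ratio was dropped as an endpoint in SAP 7.

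**Working it through.** The plan states no figure for these tables, so there is nothing to reproduce. The check is a count of who sits in each column.

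**Inputs.** N = 60 (approximate enrolment, SAP 1.1). Allocation is 1:1:1 in Period 1, 1:1 for placebo subjects in Period 2, and 1:1 for everyone in Period 3 (SAP 1.1). No dropout is assumed. The documents do not say that Period 3 randomisation is stratified by dose, so the Period 3 counts are expected values.

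**Counts.**

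- Period 1: 60/3 = 20 per arm.
- Period 2: the 20 placebo subjects split 10 and 10, so each dose column has 20 + 10 = 30.
- Period 3: each 30 splits 15 and 15, so each dose column has 15 and the Placebo column has 15 + 15 = 30.

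| Column | Period 1 | Period 2 | Period 3 |
|---|---|---|---|
| Placebo | 20, no prior HTD1801 | none | 30: 10 with 6 weeks and 20 with 12 weeks of prior HTD1801 |
| Each dose | 20, no prior HTD1801 | 30: 20 with 6 prior weeks, 10 with none | 15: 10 with 12 prior weeks, 5 with 6 |

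Only 10 of the 30 subjects in the Period 3 Placebo column were in the Period 1 Placebo column.

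**Other sample sizes.** The Period 3 Placebo column is N/2: 45 at N = 90, 31.5 at 63, 29.5 at 59 (the 42 + 17 of SAP 3.2) and 28 at 56 (if the three undosed subjects of SAP 1.1 are among the 59). The new-to-drug share of a Period 2 dose column is (N/6)/(N/3 + N/6) = 1/3 at any N. The number never exposed in the Period 3 Placebo column is 0 for every N.

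**Period 2 step.** Let continuing subjects have mean change D from Baseline at Week 6 and still D at Week 8, and let newly switched subjects have mean change d at Week 8. The column mean moves from D to (20D + 10d)/30 = (2D + d)/3, a step of (D - d)/3 towards d. For d between 0 and D (an assumption), the step lies between D/3 and 0, although no continuing subject has changed.

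**Period 3 pooling.** Let the withdrawn subjects have mean changes w500 and w1000. The Placebo column shows (15 w500 + 15 w1000)/30 = (w500 + w1000)/2. The 500 mg column minus Placebo then differs from the randomised 500 mg contrast by (w500 - w1000)/2; for 1000 mg the difference has the opposite sign. It is zero only if the two withdrawn groups behave alike. The documents give no values for either.

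**Does the grouping weaken a persisting effect?** Suppose continuing subjects show D and withdrawn subjects keep a fraction c of it. The overall columns give D - cD = (1 - c)D. Sequence groups with change from Baseline also give D - cD. With change from Week 12 they give 0 - (cD - D) = (1 - c)D. All three are equal, so the grouping makes no difference here.

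**Coverage elsewhere.** SAP 5.2.4 and 5.2.5 already give ALP, GGT, total bilirubin and, in subjects with IBD, CRP by period-defined groups with a period-specific reference value. The shift tables cover Period 2 by sequence. Protocol Table 1 schedules vital signs after Baseline only at Weeks 6, 12 and 18. What remains is the other laboratory parameters, mainly in Period 3, and vital signs at Weeks 12 and 18.

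**The case against.** A reader might infer that the table hides a persisting laboratory effect by placing it in the Placebo column. The documents do not support that. Every subject receives active drug in Period 2, so no grouping can produce a never-exposed control after Week 6. The algebra above gives the same (1 - c)D before and after regrouping, so any attenuation belongs to the withdrawal design. Nor are the Period 3 placebo subjects an invalid comparator: they are a proper randomised-withdrawal control for change from Week 12.

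The rest of the case on the other side is also substantial.

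- In Period 3 the overall columns are nearly the sequence groups already: 500 mg continuing, 1000 mg continuing, and all active to placebo, which SAP 5 itself lists. What is missing is the split of Placebo by prior dose and a clear label. This stands, and it narrows the point.
- The tables are descriptive and by visit. Untreated and withdrawn placebo subjects never share a row, and no test is planned on them. This stands, and it is why the point is minor.
- By-subject listings would let a reader rebuild the sequences. That is true, but a listing does not do the work of a summary.
- SAP 5 is ambiguous. It limits tables to groups present in the period, then says safety tables show all groups, and it marks only the pooled Period 2 groups as for efficacy alone. The intended shells may already use sequences. But SAP 5.3.2 names the overall groups for these tables, so the wording needs settling either way.

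**Conclusion.** The point holds as a minor one about table layout. Under SAP 5.3.2 as written, with 60 subjects and no dropout, one third of each Period 2 dose column (10 of 30) is newly switched from placebo. The Period 3 Placebo column (about 30) pools subjects withdrawn from both doses, all with 6 or 12 weeks of prior HTD1801. Under the planned allocation, neither dropout nor sample size can put a never-exposed subject in that Period 3 column; the one-third share assumes equal allocation and equal retention.

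The consequences are a Week 6 to Week 8 step in laboratory means that may be a change of subjects, no comparator specific to each dose in Period 3, and a label that invites a never-exposed reading beside change from pre-treatment Baseline. For vital signs only Weeks 12 and 18 are affected. The primary analysis and the planned efficacy summaries are untouched.

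**What to change.** In SAP 5.3.2, use the Placebo, 500 mg and 1000 mg columns for Weeks 2 to 6 only. For Periods 2 and 3, present laboratory and vital-sign summaries by the sequence groups in SAP 5, leaving out the pools marked for efficacy only. Show change from Week 6 (Period 2) or Week 12 (Period 3) beside change from Baseline; Protocol 8.2.4 calls for changes from Baseline to the end of the study, so that column should stay. Settle the conflicting sentences in SAP 5 on which groups appear in safety tables.

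At N = 60 without dropout, the Period 3 Placebo column of 30 becomes 15 withdrawn from 500 mg and 15 withdrawn from 1000 mg, set against 15 continuing at each dose. Each Period 2 dose column becomes 20 continuing and 10 newly switched.

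The cost is SAP wording and table shells, with more columns and smaller counts in each. No data collection or hypothesis test changes.
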